1.0 BACKGROUND

1.1 Current therapy for stage II/III rectal cancer

Tri-modality therapy with chemotherapy, radiation and surgery leads to improved outcomes for stage II/III rectal cancer and neoadjuvant chemotherapy is the current treatment paradigm to reduce toxicity and improve treatment delivery (1). Pre-operative chemotherapy has been shown to be less toxic than similar therapy given post-operatively and result in significantly higher degrees of treatment completion (2,3) and improved overall survival (4).

The optimal chemotherapy regimen for locally advanced tumors is not well-defined and differs for patients with intermediate risk, small tumor with clear circumferential radial margins (CRM), versus those with large, bulky tumors (NCCN and ESMO guidelines). Among patients with resectable tumors, short-course preoperative irradiation (25 Gy in five fractions of 5 Gy) is a standard option for stage II/III tumors and has been shown to be equivalent to chemoradiation (50.4 Gy in 28 fractions of 1.8 Gy, bolus 5-fluorouracil and leucovorin or continuous infusional fluorouracil 225 mg/m(2) per day) (5,6). The Stockholm III study demonstrated that a delay in surgery after short-course radiation is safe and reduces operative morbidity compared to immediate surgery. (7)

While current prospective trials are actively exploring novel treatments for different risk populations of rectal cancer, there are no trials of short-course radiation followed by novel systemic agents. Myerson et al (8) previously reported a 70% rate of downstaging to stage ypT0-2 among 76 patients with stage II-IV rectal cancer treated with short-course pelvic radiation followed by 4 cycles of FOLFOX prior to definitive surgery. In the NRG TNT study (NCT02921256) patients with large (T4, N2) or low tumors and are treated with 8 cycles of intravenous (IV) FOLFOX followed by long-course chemoradiation and are randomized to investigational systemic agents given in combination with long-course chemoradiation.

1.2 Potential Role for Neoadjuvant combination TAS102 plus Oxaliplatin (TASOX).

Single agent TAS102. TAS-102 is a novel type of chemotherapeutic agent being an orally available two-drug combination of a 1M Trifluoridine (FTD, a thymidine-based nucleoside analogue), and 0.5 M Tipiracil Hydrochloride (TPI). Following uptake into cells through nucleoside transporters, FTD is converted to its monophosphate F3dTMP by thymidine kinase. After further phosphorylation steps, its triphosphate F3dTTP is incorporated into DNA as substitute for thymidine triphosphate. In addition to its potent effects as an anti-metabolite as an inhibitor of thymidine synthase, FTD has additional effects causing DNA breaks (9, 10). TPI functions to inhibit degradation of FTD and thereby increases its bioavailability and TPI also exerts antiangiogenic effects by inhibiting thymidine phosphorylase (TP) (10).

Two phase III studies have demonstrated the benefit of TAS102 in patients with metastatic colorectal cancer (mCRC) refractory or not candidates for standard therapy (11,12). Compared to placebo, TAS102 improved overall survival (OS) with a Hazard Ratio of 0.56 (CI 0.44-0.71) in

patients refractory to Fluorouracil, Oxaliplatin and Irinotecan. Therapy was well tolerated and the predominant grade 3/4 toxicities were neutropenia (50%) and anemia (17%) (11). Similar benefits were seen in a more advanced population of patients refractory to 5-Fluorouracil, Oxaliplatin, Irinotecan, Bevacizumab and epidermal growth factor rector inhibitor (EGFRi) therapy with an improvement in OS [Hazard Ratio 0.68 (0.58-0.81)] and similar, predominantly hematologic toxicities. The rate of febrile neutropenia was 4% (12).

In a head-to- head trial against capecitabine, TAS102 was evaluated in TASCO1 (ClinicalTrials.gov number: NCT02743221), a multicentre, randomized, open-label, phase 2 trial (13). Patients with mCRC were randomized to TAS102 plus bevacizumab (TAS102-B) or capecitabine plus bevacizumab (C-B) as first-line therapy. The primary endpoint was progression-free survival (PFS), based on investigator assessment of radiologic images, per RECIST 1.1 criteria. Median PFS was 9.2 months with TAS102-B and 7.8 months with C-B, giving a hazard ratio (HR) of 0.71 (95% confidence interval [CI] 0.48, 1.06) for TAS102-B versus C-B. Preliminary median OS was 18 months with TAS102-B and 16.2 months with C-B giving a HR of 0.56 (95% CI 0.32, 0.98) for TAS102-B versus C-B. In pre-planned sub-group analysis, an enhanced effect of TAS102-B over C-B was seen on PFS was seen in tumors arising in the left colon and rectum, HR 0.5 (95% CI 0.31-0.82).

TASOX, Combination TAS102 and Oxaliplatin: Three phase I studies have established the safety of combination TAS102 and Oxaliplatin in mCRC (14-16) with the recommended dose of TAS102 35 mg/m2 po BID days 1-5 and oxaliplatin IV 85 mg/m2 on day 1 of a q2weekly cycle. In a dose escalation phase I, Hollebecque et al. (14) performed a two-part trial of trifluridine/tipiracil (FTD/TPI) plus oxaliplatin in patients with previously treated mCRC. A total of 17 patients were treated by at least one line of standard chemotherapy and the maximum tolerated dose (MTD) was FTD/TPI 35 mg/m2 BID with oxaliplatin 85 mg/m2. One DLT was reported at the MTD at which the patient experienced grade 3 febrile neutropenia. This patient recovered and continued with a decreased FTD/TPI dose of 30 mg/m2 BID. Patients received a mean of 7.65 treatment cycles and stable disease was achieved in eight patients. One patient previously treated with mFOLFOX6 (folinic acid-fluorouracil-oxaliplatin) achieved a confirmed partial RECIST response.

Calvo et al. (15) reported results from the dose-expansion phase on which 12 patients were administered TAS102 in combination with oxaliplatin with either nivolumab or bevacizumab. TAS102 35 mg/m2 was given BID on Days 1–5, followed q2weekly, in combination with oxaliplatin 85 mg/m2 and either nivolumab 3 mg/kg or bevacizumab 5 mg/kg, all administered on Day 1. The disease control rate was 83.3% in the safety run-in period. Neutropenia was the most common grade 3-4 treatment-related AE reported. Three (25%) patients had AE related treatment interruptions, primarily due to neutropenia. Two patients reported oxaliplatin-related grade \geq 2 neurotoxicity; one patient discontinued oxaliplatin therapy. Treatment-related deaths were not observed. Pharmacokinetic analysis revealed that FTD/TPI did not appear to be affected by co-administration of oxaliplatin.

In a third study (16), TASOX was dose-escalated in a 3+3 fashion starting at TAS102 25 mg/m² and escalating to 35 mg/m² day 1-5 using a fixed dose of oxaliplatin 85 mg/m² on day 1, q2weekly. Eligible patients previously received 5FU, oxaliplatin, irinotecan, appropriate biologics, had measurable disease, usual laboratory parameters, and ECOG PS 0-1. Among 12 patients evaluable for dose limiting toxicity (DLT), no DLTs were observed. Treatment related grade \geq 3 AEs were neutropenia (n = 4) and thrombocytopenia (n = 1). No AEs resulted in treatment discontinuation. Two patients (dose levels 2 and 3) required dose reductions for prolonged neutropenia. Median number of cycles for all treated patients was 6 ± 4. The disease control rate (DCR) at 8 weeks was 67%. Best response in all evaluable patients was 1 PR (8%) 7 (59%) SD and 4 (33%) PD.

The neoadjuvant benefit of TASOX in rectal cancer is unknown. While the most commonly chosen pre-operative therapy for stage II/III rectal cancer in North America remains capecitabine or 5-fluorouracil in combination with 50.4 Gy radiation, there is a lack of novel systemic agents being evaluated in the curative, neoadjuvant setting. The documented efficacy of TASOX in both early and advanced line therapy for mCRC justifies its application in the neoadjuvant setting where the pathologic and clinical response rate offers an early estimate of treatment benefit.

1.3 Study Overview

The study investigators hypothesize that TASOX can be safely and efficaciously delivered after short course radiation, resulting in significant pathologic downstaging, allowing for an R0 pelvic resection, and providing local control in appropriately selected stage II/III rectal cancer patients treated with contemporary TME-based surgery. It is expected that 3 months (6 cycles) of TASOX at standard doses will allow total neoadjuvant therapy introducing a new systemic agent, a shorter duration of pre-operative radiation and timely delivery of pre-operative systemic therapy. It is anticipated that if this study meets its primary endpoint, the strategy will be prospectively compared to long-course chemoradiation with capecitabine and that the reduced duration of radiation and the introduction of a new systemic agent will improve outcomes for appropriately selected patients with stage II/III rectal cancer.

In this phase II study patients will be treated with short-course preoperative irradiation (25 Gy in five fractions of 5 Gy) followed by 6 (six) 2-week cycles of TASOX followed by total mesorectal excision (TME) for patients with resectable rectal cancer (clinical T3c/dN0, T3c/dN1, T2N1). Eligible study subjects include adults who are candidates for curative intent sphincter-sparing surgery and lack high risk features such as tumor encroaching upon the mesorectal-fascia or low tumors who need an Abdominal-Perineal Resection (APR). The primary measurement of efficacy will be the Neoadjuvant Rectal (NAR) score, a validated surrogate of local and systemic disease control in stage II/III rectal cancer (17).

Figure 1. NAR Score derivation.

$NAR = \frac{[5 \ pN - 3(cT - pT) + 12]^2}{9.61}$

Fig. 1

Calculation of the neoadjuvant rectal (NAR) score. cT is an element of the set {1, 2, 3, 4}, pT is in {0, 1, 2, 3, 4}, and pN is in {0, 1, 2}. cT clinical tumor stage, pT pathologic tumor stage, pN pathologic nodal stage

The required elements of the NAR score will be prospectively collected as defined in the protocol.

[figure not shown]
2.0 OBJECTIVES

2.1 Primary Objective

The primary objective of this study is to determine whether pre-operative short-course radiation therapy (SRT) and 6 cycles of TASOX offers condensed radiation and total neoadjuvant therapy for intermediate risk rectal cancer. The primary endpoint is to achieve a reduction in Neoadjuvant Response (NAR) score compared to historic controls.

2.2 Secondary Objective

The secondary objective is to describe the adverse event profile and surgery complications among treated subjects.

2.3 Study Schema

3.0 REGISTRATION

3.1 Inclusion Criteria

- 3.1.1 Age of at least 18 years.
- **3.1.2** Newly diagnosis of rectal adenocarcinoma.
- **3.1.3** ECOG Performance Status (PS): 0, 1 or 2.

3.1.4 Candidate for sphincter-sparing surgical resection prior to initiation of neoadjuvant therapy according to the primary surgeon.

- **3.1.5** Clinical Stage: T1/N1, T2/N1, T3/N1, T3 a/b/c/dN0.
- 3.1.6 Absence of metastatic disease.
 - Clinical staging is based on physical exam by the primary surgeon, CT scan of the chest/abdomen, and pelvic MRI.
 - Node positivity determination: Entry criteria nodes will be measured in short-axis diameter and for the purposes of study entry will be considered positive if 8 mm or greater in short axis.
 - Radiographic N2 status is estimated as: 4 or more nodes that measure 8mm or more in short-axis.
 - **Radiographic N1** status is estimated as: fewer than 4 lymph nodes that measure 8 mm or greater in short axis but 1 or more lymph nodes that measure 8 mm or greater.
 - Nodal Metastatic Disease: nodal stations considered suspicious for metastatic disease (M1) for rectal cancer are common iliac, external iliac and inguinal nodes.

3.1.7 Ability to perform a curative intent sphincter-sparing TME resection at diagnosis.

3.1.8 The following laboratory values obtained ≤ 28 days prior to registration.

- Platelet count \geq 100,000/mm3
- Hemoglobin > 8.0 g/dL
- Total bilirubin ≤ 1.5 x upper limit of normal (ULN)
- SGOT (AST) < 3 x ULN
- SGPT (ALT) \leq 3 x ULN
- Creatinine <1.5 x ULN

3.1.9 Negative pregnancy test done \leq 7 days prior to registration, for women of childbearing potential only.

3.1.10 A patient of child-bearing potential is willing to employ adequate contraception. It includes any of the followings: abstinence, oral contraceptives, implantable hormonal contraceptives, or double barrier method (diaphragm plus condom). See exclusion criterion 3.2.8 3.1.11 Provide informed written consent.

3.1.12 Willing to return to enrolling medical site for all study assessments.

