3.2 Exclusion Criteria

- **3.2.1** Clinical T4 tumors.
- **3.2.2** Clinical N2 disease estimated as four or more lymph nodes that are ≥ 8 mm.
- **3.2.3** Primary surgeon indicates need for abdominoperineal (APR) at baseline.

3.2.4 Tumor is causing symptomatic bowel obstruction or patients who have had a temporary diverting ostomy are ineligible.

3.2.5 Chemotherapy within 5 years prior to registration. (Hormonal therapy is allowable if the disease free interval is \geq 5 years.)

3.2.6 Any prior pelvic radiation.

3.2.7 Any of the following because this study involves an agent that has known genotoxic, mutagenic and teratogenic effects:

- Pregnant women
- Nursing women
- Men or women of childbearing potential who are unwilling to employ adequate
- contraception

3.2.8 Co-morbid illnesses or other concurrent disease which, in the judgment of the treating investigator obtaining informed consent, would make the patient inappropriate for entry into this study or interfere significantly with the proper assessment of safety and toxicity of the prescribed regimens.

3.2.9 Patients with threatened radial margins, defined as tumors with distance of 1mm or less, or adherent to the mesorectal fascia.

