4.0 SCHEDULE OF TESTS

Test & procedures	≤ 28 days pre- registration	≤60 days prior to therapy	Prior to each cycle TASOX, - 3 days ¹	Pre-op visit after completion of cycle 6 TASOX, ie. ≤ 56 days after day 14, cycle 6 ^{8,10,12}	Post- Surgery 2-8 weeks post - op
History and physical	X		X	X	X
Pulse, BP and temperature	X		X	X	x
ECOG			X	X	X
Weight	Χ		X	X	X
Height	Χ				
Adverse Events ¹⁰			X	X	
Hematology ²	Χ		X	X	
Chemistry ³	Χ		X	X	
CEA	Χ		X	X	X
Pregnancy test ⁴	X		X— cycle #1 only		
Pathology confirmation of rectal adenoca.		$\mathbf{x} \leq 90 \text{ days}$			
Rectal exam and proctoscopy ⁵		X			
MRI of pelvis ^{6,8}		X		x ^{11,8}	
CT Chest or chest Xray ^{7,8}		X			
CT of abdomen with contrast ^{7,8}		X			
Documentation of post-operative complications- see					X
Section 6.4.					

1. Recommendations for timing of therapy:

- Radiation must commence within 3 weeks of study registration.
- Chemotherapy with TAS-102 must begin within 1-3 weeks after completion of radiation.

- Patients must have assessment at the time of progressive disease, study withdrawal, or removal.

2. Hematology includes hemoglobin, platelets and absolute neutrophil count (ANC).

3. Chemistry includes SGOT (AST), SGPT (ALT), total bilirubin, creatinine.

4. Urine or serum pregnancy test per institutional standard required for females of childbearing potential \leq 7 days of registration.

5. Rectal exam and proctoscopy are ideally to be performed by the primary surgeon. Proctoscopy should be performed \leq 90 days prior to registration or after registration but before the start of treatment. Proctoscopy may be accomplished using rigid proctoscopy or as part of a flexible sigmoidoscopy or colonoscopy.

6. Pelvic MRI Scan, with or without contrast per treating investigator/institutional standards, is to be performed within 60 days prior to treatment start. Use same imaging modality throughout the study.

7. A PET/CT scan may be performed in lieu of a CT scan with contrast, but a CT scan is preferred.

8. Scans do not have to be performed at the trial site; they can be performed at other locations as long as images are available for review. Scan is to be performed within </= 60 days prior to registration. Contrast is preferred but not required for the CT of the chest. Contrast is required for the CT of the abdomen.

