5.0 REGISTRATION PROCEDURES

To be completed after eligibility determination and at least 24 hours prior to first day of radiation therapy. It will be done by completing the registration form and emailing the following information to [contact].

All the following information will be required:

- Name of institution.
- Patient initials.

- Age.
- Sex.
- Race.
- Date of diagnosis.
- Informed consent signed date.
- Projected treatment start date. i.e., start date of radiation therapy.

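### The pregnancy test is dated to registration, so the first pelvic radiation fraction may be given on a negative test up to 28 days old, with no repeat until radiation is over

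*Combined protocol and SAP*

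**What the plan says.** **Entry test.** Criterion 3.1.9 asks for a negative test at most "7 days prior to registration, for women of childbearing potential only". Footnote 4 of section 4.0 (Schedule of Tests) uses the same anchor: "Urine or serum pregnancy test per institutional standard required for females of childbearing potential", again within 7 days of registration.

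**First exposure.** Section 5.0 identifies the start of treatment with radiation: "Projected treatment start date. i.e., start date of radiation therapy". It requires registration at least 24 hours beforehand. Footnote 1 sets the upper limit: "Radiation must commence within 3 weeks of study registration". Section 6.0 gives the same limit.

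**Repeat test.** The pregnancy row has one further entry, for cycle 1 only, in the column for visits up to 3 days before a TASOX cycle. Footnote 1 places that cycle after radiation: "Chemotherapy with TAS-102 must begin within 1-3 weeks after completion of radiation".

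**Other safeguards.** Criterion 3.2.7 excludes pregnant women "because this study involves an agent that has known genotoxic, mutagenic and teratogenic effects". Criteria 3.1.10 and 3.2.7 require adequate contraception.

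**Other baseline tests.** Footnote 6 dates the pelvic MRI to treatment (it "is to be performed within 60 days prior to treatment start"). Footnote 5 lets proctoscopy be done before registration "or after registration but before the start of treatment".

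**The concern.** An entry test supports eligibility. A pre-exposure test protects the patient on the day, and for that its age at the exposure matters. The protocol accepts this for the drugs, since it repeats the test before cycle 1. It does not do so for radiation, which comes first and cannot be undone: five fractions of 5 Gy to the pelvis.

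Two kinds of pregnancy could be missed: one conceived after the registration test because contraception failed, and one too early to show at that test. In either case the schedule next looks after the whole radiation course has been delivered. The printed reason in 3.2.7 names an agent and does not mention radiation, which may explain why only the drugs have a test close to exposure.

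At stake is the safety of a small number of participants. The NAR score, the sample size of 27 and the primary analysis do not depend on it.

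**Working it through.** The plan states no figure for the age of the test at first exposure, so there is none to reproduce. The check is calendar arithmetic on its own windows.

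**Inputs**
- Test to registration: 0 to 7 days (3.1.9, footnote 4).
- Registration to first fraction: 1 day (24 hours, section 5.0) to 21 days (3 weeks, footnote 1 and section 6.0).
- Radiation course: five fractions, normally over 5 to 7 days, with a spread over two weeks allowed (section 6.1).
- End of radiation to cycle 1: 7 to 21 days (footnote 1).
- Repeat-test window: up to 3 days before cycle 1 (section 4.0).

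**Age of the last required test at the first fraction** = (test to registration) + (registration to fraction 1)
- Maximum: 7 + 21 = 28 days.
- Test on the day of registration, latest start: 0 + 21 = 21 days.
- Minimum: 0 + 1 = 1 day.

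The 28 days is this sum. It does not come from the heading of the 28-day pre-registration column, which 3.1.9 and footnote 4 narrow to 7 days for this test.

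**Earliest repeat after the last fraction** = 7 − 3 = 4 days. The latest is 21 days, if the test is done on the day of a cycle 1 started at the limit.

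**Longest interval between the two required tests**, counting the first fraction as day 1 of the course, = 7 + 21 + (course length − 1) + 21
- 5-day course: 7 + 21 + 4 + 21 = 53 days.
- 7-day course: 7 + 21 + 6 + 21 = 55 days.
- 14-day course: 7 + 21 + 13 + 21 = 62 days.

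**Search for a test in between.** The schedule has no radiation-start visit and no pregnancy test in the column for the 60 days before therapy. Sections 5.0, 6.0 and 6.1 require none. The section 2.3 schema is not shown and the consent pages were removed, so the statement covers the visible text only.

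**Effect of the change.** With a test required within 7 days before fraction 1, the maximum age falls from 28 to 7 days; with a 3-day window it would be 3 days.

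**The case against.** The best counter-arguments concern weight and supporting detail; the gap itself is not in dispute.

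- **It is a corner case with safeguards in place.** Reaching 28 days needs both the earliest test and the latest start, radiation may begin 24 hours after registration, and exclusion, entry test, contraception and cycle 1 test all apply. This stands as a reason to expect a rare event. It does not close the gap: nothing triggers a retest when the start is late, and the protocol itself does not treat contraception as enough before the drugs.
- **Dating to registration is common in this protocol.** The eligibility bloods (3.1.8) may be 28 + 21 = 49 days old at the first fraction, and footnote 8 also dates scans to registration, which weakens the comparison with the MRI. Footnote 5 adds flexibility and does not demand a fresh result. This is largely fair. The comparison is secondary, and the point rests on 3.1.9, footnotes 1 and 4, and the pregnancy row.
- **The reason printed in 3.2.7 changes no one's protection.** True. Pregnant women are excluded whatever the rationale.
- **The 4-day figure depends on footnote 1**, whose heading calls its timings recommendations. Section 6.0 gives no minimum gap before TASOX. If cycle 1 began the day after a 5-day course (day 6), the 3-day window would reach back to day 3. The repeat would still follow the first fraction.
- **The planning CT in section 6.1 precedes the first fraction.** True. Its dose is far smaller than treatment, but it bears on where the sponsor places the test.
- **Radiotherapy departments may test anyway.** Possibly, but the visible text does not require it. The reference to institutional standard in footnote 4 reads most naturally as the choice between urine and serum.

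**Conclusion.** The concern holds. The visible protocol permits the first pelvic fraction on a negative pregnancy test up to 28 days old, or up to 21 days old even when the test was done on the day of registration. Under footnote 1, the next scheduled test comes no sooner than 4 days after radiation has ended.

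These are limits of permitted windows, not typical values; the documents do not say how start dates are distributed. They assume that the windows are applied as written and that the schema and consent pages add no test. The event is expected to be rare. Its frequency cannot be estimated, because the documents do not say how many of the 27 patients will be women of childbearing potential. The change is worth making because the possible harm is serious and irreversible and the remedy costs very little. No statistical element of the plan is affected.

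**What to change.** Keep the registration test for eligibility and the cycle 1 test before the drugs. Amend three places (criterion 3.1.9, footnote 4 and the pregnancy row of the Schedule of Tests) so that a negative test must also be dated within 7 days, or another interval the sponsor sets, before the first radiation fraction. Repeat it only if the registration test is older than that. The sponsor may choose to place this test before the planning CT, provided it is still within the interval at the first fraction.

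The 7 days is a proposal borrowed from the protocol's own entry window; no document sets a maximum test age before radiation. Sites already record the projected radiation date at registration (section 5.0), so they can see in advance who will need the repeat.

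**Cost.** A small wording amendment, and at most one extra urine or serum test for each woman of childbearing potential whose registration test has passed the interval. Other patients are unaffected. The change shortens the gap but cannot exclude a pregnancy too early to detect, so the contraception requirement stays.
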